10.5.5. Other Data Assessments

Technically successful treatment definition

A technically successful treatment will be defined by the presence of an ablation zone, ground glass opacity, or frank consolidation encompassing the targeted index tumor(s) no later than the 1 month follow up visit after the cryoablation procedure. Technical success will be analyzed on a per tumor basis.

Disease recurrence or progression definitions

The reference date for disease progression evaluation will be associated with the initial (first) cryoablation procedure done per study protocol. In the event of multiple cryoablation procedure dates, such as with bilateral lesions or staged treatments, the date of reference for disease progression evaluation will be the initial (first of n) cryoablation procedure.

- **Local disease progression** will be determined locally by evidence of local tumor failure.
- **Lung-disease-specific survival rate** is defined as the time in days from the first cryoablation procedure to death and **a)** the date of metastatic lung tumor progression (new lung tumors or local tumor failure of the index tumor), **b)** the date of death with local control of the index tumor, or **c)** the date of last follow up in patients who were still alive with local tumor control of the index tumor. Patients who are alive will be censored at the date of their last visit. Patients who have died from causes other than local failure of the index tumor will be censored at the time of death. Lung disease-specific survival rates will be summarized by using Kaplan-Meier methodology.
- **Overall survival rate** is defined as the time in days from the first cryoablation procedure to death. Patients who are alive will be censored at the date of the last visit. Overall survival rates will be summarized by using Kaplan-Meier methodology.
- **Time to metastatic lung disease progression beyond the index tumor** is defined as the time in days from the first cryoablation procedure to metastatic disease beyond the index tumor site. Patients without metastatic lung disease progression will be censored at the date of their last visit or their date of death (due to any cause). Metastatic progression free survival rates will be summarized by using Kaplan-Meier methodology.

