Efficacy of cryoablation on local tumor control for each index tumor in patients with pulmonary metastatic disease undergoing additional cryoablation treatment(s) of a previously treated index tumor will be summarized using the proportion of tumor control at 12-months post re-treatment and a 95% CI.

Technically successful treatment

A technically successful treatment will be defined by an ablation volume, ground glass opacity, or frank consolidation encompassing the targeted index tumor(s) within 30 days of the cryoablation procedure. Technical success will be calculated on a per-tumor level as well as a patient level. To be considered a technical success on a patient level all tumors treated during the baseline procedure must meet the technical success criteria. Technical success rates and 95% CIs will be calculated using random effects logistic regression on a tumor level and logistic regression on a patient level.

Disease recurrence or progression

The reference date for disease progression evaluation will be associated with the initial (first) cryoablation procedure done per study protocol. In the event of multiple cryoablation procedure dates, such as with bilateral lesions or staged treatments, the date of reference for disease progression evaluation will be the initial (first of n) cryoablation procedure.

- **Local disease progression** will be determined locally by evidence of local tumor failure. Time to lung disease progression will be summarized by using Kaplan-Meier methodology.
- **Lung-disease-specific survival** rate is defined as the time in days from the first cryoablation procedure to death and **a)** the date of lung tumor progression (new lung tumors or incomplete response), **b)** the date of death without lung tumor progression, or **c)** the date of last follow up in patients who were still alive without lung tumor progression. Patients who are alive will be censored at the date of their last visit. Patients who have died from causes other than lung cancer will be censored at the time of death. Lung disease-specific survival rates will be summarized by using Kaplan-Meier methodology.
- **Overall survival** rate is defined as the time in days from the first cryoablation procedure to death. Patients who are alive will be censored at the date of the last visit. Overall survival rates will be summarized by using Kaplan-Meier methodology.

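### Lung-disease-specific survival has conflicting definitions in the SAP and the protocol, and two time-to-progression outcomes that censor deaths are labelled progression free survival

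*SAP*

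**What the plan says.** **Lung-disease-specific survival, SAP (Disease recurrence or progression).** Time runs from the first cryoablation to death and one of three dates. Clause a) is "the date of lung tumor progression (new lung tumors or incomplete response"; clause b) is death without lung progression; clause c) is "the date of last follow up in patients who were still alive without lung tumor progression". Two censoring sentences follow: "Patients who are alive will be censored at the date of their last visit" and "Patients who have died from causes other than lung cancer will be censored at the time of death".

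**Lung-disease-specific survival, protocol 10.5.5.** The structure is the same but the terms differ. Progression in clause a) is "new lung tumors or local tumor failure of the index tumor". Clause b) is "the date of death with local control of the index tumor" and clause c) is "the date of last follow up in patients who were still alive with local tumor control of the index tumor". Living patients are censored in the same unqualified way as in the SAP. Deaths are censored unless they come from local failure of the index tumor.

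**Related definitions.** Protocol 8.7 has four response categories (complete response, partial response, stable disease, local failure) and defines local tumor control as absence of local failure. Protocol 6.3.1 excludes primary lung cancer as an index tumor. The SAP bullet just before the one at issue says that local disease progression "will be determined locally by evidence of local tumor failure".

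**The two progression outcomes.** Time to metastatic lung disease progression beyond the index tumor and time to overall cancer progression are worded alike in both documents. Patients without progression are censored at last visit or at death from any cause. The Kaplan-Meier results are then named metastatic, or overall cancer, *progression free survival* rates.

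**The concern.** An outcome should have one event rule and one censoring rule. Here the protocol and the SAP give different rules for the same named outcome, and each leaves part of its own rule open. Two analysts could each follow a document faithfully and draw different curves from the same data, and a choice made at analysis would be made with the results in view.

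The label on the two progression outcomes is a separate matter. Progression free survival is normally read as the proportion alive and without progression. A Kaplan-Meier estimate that censors deaths is something else. In a single-arm study such rates can only be read against other series, so the name affects how the result is understood.

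**Working it through.** The documents state no figure for any of these outcomes, so there is none to reproduce. The check is a comparison of the texts, followed by a short derivation for the label.

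**1. The definitions side by side**

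| Element | SAP | Protocol 10.5.5 |
|---|---|---|
| Progression, clause a) | New lung tumors or incomplete response | New lung tumors or local failure of the index tumor |
| Condition in clauses b) and c) | No lung progression | Local control of the index tumor |
| Deaths censored | Not due to lung cancer | Not due to local failure of the index tumor |
| Living patients | All censored at last visit | All censored at last visit |

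The first three rows differ. The SAP revision history names no change to this definition; its only possible reference is a general remark that more specific methods were added.

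**2. Applying the rules to patients**

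- *Alive, index tumor stable or in partial response, no new tumor.* Protocol: censored under c). SAP: clause a) taken literally gives a progression date, but the sentence on living patients censors. The SAP text pulls both ways.
- *Alive, new lung tumors, index tumor controlled.* SAP: clause a) applies and c) does not, yet the sentence on living patients censors. Protocol: a) and c) both fit, and the same sentence censors.
- *Died of new lung metastases, index tumor controlled.* Protocol: a) and b) both fit, and the death sentence censors at death. SAP: not censored by the death sentence if lung cancer means lung metastases; censored by it if the term means primary lung cancer.
- *Died of local failure of the index tumor.* Protocol: not censored by the death sentence. SAP: the same only if lung cancer includes metastases.
- *Alive, complete response, no new tumor.* Censored in both.
- *Died of an unrelated cause without lung progression.* Censored by the death sentence in both.

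The documents agree on the last two types. The others conflict or depend on how an undefined term is read.

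**3. Direction of the label error**

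At each event time tᵢ let nᵢ be the number at risk, pᵢ the progressions, and mᵢ the deaths without progression.

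- As planned, deaths censored: R(t) = ∏(1 − pᵢ/nᵢ).
- Alive and progression-free, deaths counted: P(t) = ∏(1 − (pᵢ + mᵢ)/nᵢ).

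A patient leaves the risk set at the earliest of progression, death or last visit in either analysis, so the nᵢ are the same. Each factor of P is no larger than the matching factor of R, hence P(t) ≤ R(t). The inequality is strict from the first death without progression, as long as R(t) is above zero. This needs no assumed rate and no independence assumption. The gap R − P depends on pᵢ and mᵢ, for which the documents give no planning values.

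**4. What is not touched**

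The primary design reproduces: with 203 tumors and rejection at 181 or more, alpha is 0.0239 and power 0.8501, and 203/0.90 = 225.6, rounded up to 226. None of the definitions above enters that calculation, the 12-month local control endpoint, or overall survival.

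**The case against.** The strongest reply is that this is a drafting slip in a minor outcome. Complete response requires disappearance or at least a 75% decrease from the month 1 sum, so a literal reading would have many well-controlled tumors counted as progressing. The neighbouring SAP bullet uses local failure, and SAP clauses b) and c) speak of lung progression. No sensible analyst would code stable disease as progression. Lung-disease-specific survival is not named in the list in protocol 5.3 (which is not exhaustive), and nothing here is tested.

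Much of that stands. A reader might infer that the SAP turns living patients with stable disease or partial response into events. The documents do not support this, because the SAP also censors all living patients; the result is an unclear rule, not a clean event. The slip explanation does not, however, resolve the different death-censoring rules, the different conditions in b) and c), or the status of living patients with progression.

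On the label, the reply is that both documents use the same words, head the outcomes as time to progression, and disclose the censoring of deaths in the preceding sentence. That is correct: it is not a discrepancy between documents, and censoring deaths is a valid choice for time to progression. What remains is that the name given to the reported rate describes a different quantity.

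**Conclusion.** The point holds as a conflict of definitions plus a mislabelled estimate, and it should be corrected. Lung-disease-specific survival cannot be computed unambiguously from the two documents: progression, the deaths to be censored, and the status of living patients with progression all need a single rule. The two progression outcomes are sound as time to progression, but their name overstates the proportion alive and progression-free whenever patients die without progression.

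The direction of the label error is certain; its size cannot be derived. A reader might try to size it from the 1-year survival of 89.4% in a series cited in protocol 3.2. That figure includes deaths after progression. It also comes from 20 patients selected for ECOG 0 to 1, life expectancy above 1 year and no active extrapulmonary metastasis, whereas this trial admits KPS of 60 or more and life expectancy above 3 months. It neither estimates nor bounds the gap here. The effect on lung-disease-specific survival cannot be sized either.

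Nor should the point be read as a threat to the trial's main conclusion. These are supportive outcomes without a hypothesis test.

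**What to change.** **Lung-disease-specific survival.** State one operative definition in the SAP and note there that it departs from protocol 10.5.5:

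- replace *incomplete response* with local failure of the index tumor (protocol 8.7.4);
- replace *lung cancer* as cause of death with metastatic lung disease;
- limit the censoring of living patients to those without lung progression;
- because progression is then an event, rename the outcome so that it is not presented as disease-specific survival, for example time to lung progression or death from metastatic lung disease. Deaths from other causes without earlier lung progression stay censored.

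**The two progression outcomes.** Keep the analysis and replace *progression free survival* with freedom from progression (deaths censored).

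**Cost.** Wording in the SAP, slightly more analysis work, and possibly queries to sites on cause of death; the documents do not show whether it is captured in the form needed. Sample size, alpha and the primary analysis do not change.

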7. STUDY PROCEDURES

The study schedule of events and the specific procedures performed at each visit are shown in Table 1, Schedule of Events. Each patient will undergo a total of 9 visits, including an initial/screening visit, the procedure visit, and 7 post-operative visits. More visits may be required when medically necessary.

Table 1: Schedule of Study Events

Procedures	Screening ^a	Procedure Date	W 1 ^c	M 1 ^e	M 3 ^{g,h,i}	M 6, 12, 18, 24 or W/D ^{g,h,i}
Informed Consent	X					
Inclusion/Exclusion	X					
Demographics	X					
Targeted Medical History	X					
Karnofsky Performance	X			X	X	X
Pertinent Medication	X		X	X		
Discontinue anticoagulation, as clinically indicated	X	X				
Imaging Scan	X ^f		X ^d	X ^f	X ^f	X ^f
Record index tumor characteristics	X					
Cryoablation procedure		X ^b				
Labs	X					
Quality of Life (SF-12)	X			X	X	
Safety Assessment		X	X	X	X	X

^a All screening visit requirements should be within 8 weeks of the initial cryoablation procedure. Any items (e.g., imaging or lab assessment) previously conducted as routine standard of care prior to the signed informed consent may be used to satisfy the screening requirements provided they are completed within 8 weeks of the initial cryoablation procedure.

^b If multiple tumors are planned for study inclusion, treatment of all study index tumors should be completed within an 8 week window.

^c The week 1 follow up visit may take place prior to discharge from the hospital or within 1 week (7 days) of the cryoablation procedure.

^d Week 1 imaging may be a chest CT ± contrast or chest X-Ray

^e Month 1 visit window 30 days -7/+21 days

^f Chest CT scan ± contrast (contrast is preferred)

^g Months 3, 6, 12, 18 and 24 visit window +/- 30 days

^h In the event of multiple cryoablation procedure dates, the most recent procedure date will serve as the reference for determining the follow up visit window.

ⁱ While return visits are preferred to be conducted in the clinic setting, in the event the patient is not able to return due to distance or illness, follow up assessments (i.e. all assessments with the exception of imaging) may be conducted via telephone or tele-video (e.g. Skype). Tele-video should only be considered if the patient has the knowledge and access to such technology.

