- **Time to metastatic lung disease progression beyond the index tumor** is defined as the time in days from the first cryoablation procedure to metastatic disease beyond the index tumor site. Patients without metastatic lung disease progression will be censored at the date of their last visit or their date of death (due to any cause). Metastatic progression free survival rates will be summarized by using Kaplan-Meier methodology.
- **Time to overall cancer progression** is defined as the time in days from the first cryoablation procedure to cancer progression (i.e., any location of active cancer disease). Patients without cancer progression will be censored at the date of their last visit or their date of death (due to any cause). Overall cancer progression free survival rates will be summarized by using Kaplan-Meier methodology.
- **Time to untreatable metastatic lung disease control with cryoablation** is defined as the time in days from the first cryoablation procedure to the time when the metastatic lung disease cannot be treated with cryoablation. Overall time to untreatable metastatic lung disease progression rates will be summarized by using Kaplan-Meier methodology.
- **Time to untreatable metastatic lung disease control with focal therapy** is defined as the time in days from the first cryoablation procedure to the time when the metastatic lung disease cannot be treated by focal (e.g., ablation, surgery, SBRT) intervention for control of metastatic lung disease. Overall time to untreatable metastatic lung disease progression rates will be summarized by using Kaplan-Meier methodology.

Intra-procedural data

Initial cryoablation procedure information including the type of procedure, tumor size and number, cryoablation needle type and the number of each type of needle used, freeze and thaw times, procedure times, and anesthesia type will be summarized using descriptive statistics.

Physical performance and quality of life

Physical performance (KPS) and quality of life (SF-12) assessments will be made by examining the change in the baseline scores to those reported post-operatively and at follow-up visits. The KPS scale and each of the eight SF-12 domains will be summarized at each time point by descriptive statistics. Percent change from baseline for each measure will also be summarized by descriptive statistics.

Additional Data Summaries

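### Time to metastatic lung progression is censored at the last visit, which may be a phone contact without a scan, so unscanned time can count as progression-free

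*SAP*

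**What the plan says.** The SAP (Disease recurrence or progression) defines time to metastatic lung disease progression beyond the index tumor as days from the first cryoablation. Its censoring rule reads: "Patients without metastatic lung disease progression will be censored at the date of their last visit", or at death from any cause. The result is labelled as a progression-free rate: "Metastatic progression free survival rates will be summarized by using Kaplan-Meier methodology". Time to overall cancer progression, which covers active cancer at any location, has the same rule. Protocol section 10.5.5 repeats both rules. Lung-disease-specific survival in the SAP uses "the date of last follow up in patients who were still alive without lung tumor progression" as one of its end dates.

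Protocol section 8.6 schedules chest CT or FDG-PET-CT at months 1, 3, 6, 12, 18 and 24. Table 1, footnote i, applies to the month 3 column and to the column for months 6 to 24 or withdrawal. For patients kept away by distance or illness it says that "follow up assessments (i.e. all assessments with the exception of imaging) may be conducted via telephone or tele-video". Sections 7.6 and 7.7 list the progression assessment separately from the CT.

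No passage defines a visit as one with a scan, or refers to the last evaluable scan as a censoring date. Section 7.9 asks patients who terminate early for a final CT only if they are physically able to return. The sensitivity analyses under Handling of Missing Data in the SAP concern the primary endpoint only.

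**The concern.** A new lung metastasis without symptoms is found on a scan. If a patient is no longer scanned but is still phoned, the last phone date can become the censoring date. The interval since the last scan is then counted as observed and free of progression. A patient last scanned at month 6 and phoned until month 24 would contribute 18 such months. Censoring at death has the same gap: the time from last scan to death counts as progression-free.

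In a single-arm study the absolute Kaplan-Meier rate is what readers will take away, since no concurrent control shares the bias. Illness is one of the two reasons the footnote names for a remote visit, so the patients affected may also be those at higher risk of progression.

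**Working it through.** The documents state no progression rate, event count or power for this outcome, so there is no figure of theirs to reproduce. The check below gives direction and an illustrative size.

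**From the documents:** the scan schedule (protocol 8.6), remote visits from month 3 (Table 1, footnote i), and censoring at last visit or death (SAP; protocol 10.5.5).

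**Assumed:** exponential time to progression with a 12-month median; a share p of patients has no scan after month L but is contacted until month 24; no progression is learned remotely; no deaths or other losses.

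1. S(t) = 0.5^(t/12), so S(6) = 0.707, S(18) = 0.354 and S(24) = 0.250.
2. Under last-visit censoring nobody leaves the risk set before month 24, so the Kaplan-Meier rate at 24 months is a simple proportion: (1 − p) × S(24) + p × S(L). The overstatement is p × [S(L) − S(24)].
3. If only the month-24 scan is missed (L = 18), this is p × 0.104. If no scan follows month 6 (L = 6), it is p × 0.457.

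| Share affected | Only month-24 scan missed | No scan after month 6 |
|---|---|---|
| 5% | 25.5% (+0.5 points) | 27.3% (+2.3) |
| 10% | 26.0% (+1.0) | 29.6% (+4.6) |
| 20% | 27.1% (+2.1) | 34.1% (+9.1) |

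4. Censoring the affected patients at their last scan (L = 6) gives 0.707 × (0.250/0.707) = 0.250. There is no bias if they progress at the same rate as the others.
5. If their hazard doubles after month 6, their 24-month rate is 0.707 × (0.250/0.707)² = 0.088. At p = 10% the truth is 0.9 × 0.250 + 0.1 × 0.088 = 23.4%. Last-visit censoring still gives 29.6% (6.2 points too high). Last-scan censoring gives 25.0% (1.6 points too high).
6. Counting all affected patients as progressed gives 0.9 × 0.250 = 22.5%. In this example that figure and last-scan censoring bracket the truth.

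A simulation on the protocol's scan schedule (200,000 patients per scenario) varied the assumptions: 12-month progression of 30% or 50%, 5% to 30% of patients phone-only from a random visit onward until month 24, and hazard unchanged or doubled. Last-visit censoring was biased upward in every scenario, by 1.5 to 16.8 points at 24 months. Last-scan censoring was biased by about 0 with unchanged hazard and by 0.8 to 5.4 points with doubled hazard.

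**The case against.** The case against has four parts.

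**Imaging is not waived.** Footnote i only says that imaging cannot be done remotely. Table 1 still marks a scan at every follow-up visit, the scan could be done elsewhere, and protocol deviations are summarized. A reader might infer that the protocol endorses visits without scans; it does not go that far. What stands is that no rule requires a scan before a contact can set the censoring date. If scans are always obtained, the change costs nothing.

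**Remote visits are not blind.** A reader might infer that no event can be recorded by phone. The documents do not support that, since remote visits still include assessments of lung progression, local recurrence, systemic treatment and local therapy. Progression known from outside scans can be recorded. The calculation sets this to zero, so for a given share of patients and length of unscanned time it overstates the bias.

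**Long unscanned runs may be uncommon.** Patients entering hospice are documented as early terminations, and those given another local treatment to an index tumor are withdrawn. Both limit 18-month phone-only follow-up. The month-6 column is therefore near a worst case, and a reader should not take 30% or 34% as the expected result. A missed scan followed by a later one only delays the event date.

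**Last-scan censoring is not a universal remedy.** This also stands. Overall cancer progression covers any location while scheduled imaging is of the chest, so the last chest scan is not the right limit of observation there. Lung-disease-specific survival mixes death and progression, and giving one patient two censoring dates within it would not work. Last-scan censoring also leaves bias when the sickest patients stop scanning, as steps 5 and 6 show.

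**Conclusion.** The point holds for time to metastatic lung disease progression beyond the index tumor. As written, the censoring rule can count time after the last scan as progression-free, and this pushes the Kaplan-Meier rate upward. Time to overall cancer progression has a related weakness, because a phone contact alone can end its follow-up, but it needs a different limit of observation.

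The size is unknown. With a 12-month median, 10% of patients affected and no progression learned remotely, the 24-month overstatement runs from about 1 to about 4.6 points, depending on how many scans are missed. It is smaller if remote visits are rare or outside findings are recorded, and larger if more patients are affected or those affected progress faster.

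A reader might infer that the trial's efficacy conclusion is at risk. It is not: the outcome is supportive, has no hypothesis or performance goal, and does not enter the primary test against 84%.

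**What to change.** In the SAP (Disease recurrence or progression) and protocol section 10.5.5:

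- **Time to metastatic lung progression beyond the index tumor:** censor patients without progression, including those who die without it, at the last evaluable chest CT or FDG-PET-CT showing no progression. Progression documented from any source still counts as an event.
- **Time to overall cancer progression:** censor at the last disease assessment adequate to detect progression, whether imaging or a documented clinical or oncology evaluation. Do not use a phone contact alone.
- **Sensitivity analysis:** count death or loss to follow-up after missed scans as progression. State in advance the date assigned to these events, and whether patients still phoned but no longer scanned are treated as lost.
- **Leave unchanged:** last contact as the censoring date for overall survival, and a single censoring date within lung-disease-specific survival.

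The cost is a short edit to both documents, a different date variable for two outcomes and one added analysis. Scans are scheduled study procedures, so no new visits are needed. Reported progression-free rates may be slightly less favorable, and some follow-up time is lost.
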